We designed this study to elucidate the role of metformin and combination of metformin and pioglitazone in reducing the levels of interleukin-6 and interleukin-8 in patients with PCOS. This will help us in deciding a better treatment regimen for patients with PCOS. Interleukin-6 and interleukin-8 may emerge as predictive biomarkers of treatment response.

2. Aims and objectives

OBJECTIVES:

The objectives of this study are

1. Primary

To investigate the changes in the levels of interleukin-6 and interleukin-8 after 3 months treatment with metformin alone and combination of metformin and pioglitazone in patients with PCOS.

2. Secondary

To evaluate insulin resistance in all the groups at baseline and after 3 months of treatment.

3. Hypothesis:

Combination of metformin and pioglitazone may decrease the levels of IL-6 and IL-8 in women with PCOS better than metformin.

4. Operational Definitions:

POLYCYSTIC OVARIAN SYNDROME: Polycystic ovarian syndrome, or PCOS, is a condition characterized by chronic oligo-anovulation, polycytic ovaries and hyperandrogenism.

METFORMIN: An oral hypoglycemic drug that decreases glucose production by the liver

and increases peripheral glucose uptake, used to treat type 2 diabetes.

PIOGLITAZONE: is a thiazolidinedione (TZD) with hypoglycemic (antihyperglycemic, antidiabetic) action to treat diabetes.

INTERLEUKIN-6 is a cytokine that acts as both a pro-inflammatory cytokine and an antiinflammatory myokine. It is in humans encoded by the IL6 gene (5).

INTERLEUKIN-8: is a chemokine produced by macrophages and other cell types such as epithelial cells, airway smooth muscle cells (6) and endothelial cells.

5. Materials and Methods:

a. STUDY DESIGN: Two-Arm Randomized Clinical trial.

b. STUDY SETTING: OPD patients in Mardan Medical Complex, Khyber Medical University

c. STUDY DURATION: Six Months after approval of proposal

d. SAMPLE SIZE:

The sample size was calculated using OpenEpi software. With an expected reduction in interleukin-6 and interleukin-8 values of 15% in the Metformin arm, we would need 102 women with PCOS to demonstrate a 40% reduction in interleukin-6 and interleukin-8 in the Metformin and Pioglitazone arm with a power of at least 80% and a ratio of 1 in the two arms.

Arm#1: 51 women with PCOS will be selected based on the inclusion and exclusion criteria. They will receive metformin according to the body weight with maximum dose of 1000 mg (BD) daily.

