7.2.5 Treatment discontinuation

The treatment of the patient or study on the subject will be discontinued in case of pregnancy or any disease given in exclusion criteria and in patient with hypersensitivity to drugs. There is no serious adverse effect observed after treatment discontinuation.

8. Assessment Plan: HISTORY RELATED QUESTIONS AND CLINICAL ASSESSMENT

Name:	Age:	Date:	
Addres	ss: Marital status:		Phone No:
•	Menstrual irregularity:		
•	Age of menarche:	_	
•	Hirsutism:		
•	Acne:		
•	Daily physical exercise:		
•	Infertility:		
•	Height (m)		
•	Weight (kg)		
•	BODY MASS INDEX (kg/m2):		_
•	Drug history (current and past me	dications)	:
•	Surgical history:	_	
•	BP:		

_

Pulse: _____

Schedule of assessments

	Screening	Baseline investigations	On treatment	End of treatment	
	14-21 days prior to registration	Within 7 days prior to registration	Within 3 days prior to first dose	After 3 months	
Informed consent					
Clinical assessment (mentioned above) Pelvic ultrasound					
right ovary and left ovary (10 or more follicles. 2 – 9 mm in diameter)					
Other imaging					
FBS RBS					
LH FSH Testosterone					
IL-6 IL-8					
HOME. IR					
Concomitant medications					
Adverse events					
Outcome events					

ASSESSMENT PHASE DEFINITONS AND SPECIAL CIRCUMTANCES

SCREENING

All screening will be done before registration of the patients.

BASELINE

All baseline investigations including (but not limited to) levels of interleukin-6 and interleukin-8, insulin resistance and pelvic ultrasound will be performed before giving treatment to the patient.

ON TREATMENT

Assessment during the treatment will be performed.

END OF TREATMENT

All baseline investigations including (but not limited to) levels of interleukin-6 and interleukin-8, insulin resistance and pelvic ultrasound will be performed 12 weeks after treatment.

FOLLOW UP AFTER TREATMENT

No follow up will be performed.

9. Outcomes and Endpoints:

The outcomes of the study is the change in the levels of interleukin-6 and interleukin-8 with the use of antidiabetic drugs (metformin alone and combination of metformin and pioglitazone). Other symptoms like hirsutism, polycystic ovaries and serum testosterone levels may decrease and menstrual cycles might become become regular.

10. Safety Reporting: PREGNANCY

Follow up in the treatment will be discontinued with pregnancy.

REPORTING OF SERIOUS ADVERSE EVENTS

Any adverse effects that occur during the treatment will be reported.

11. Treatment Information:

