Metformin with the trade name of Glucophage is manufactured by Merck International Pharmaceutical Company Limited. Metformin plus Pioglitazone combination with the trade name of Zolid plus is manufactured by Getz Pharmaceutical Company Limited. We would consistently use these two brands. The dosage will be according to according to body weight.

Cost bearing: The cost of the medicines and investigations will be provided to the study participants by the project managers ([name] and [name])

12. Data Analysis Procedure:

Mean ± SD will be used for numeric data generated from our work. In each arm the mean difference in the interleukin-6 and interleukin-8 values will be calculated using paired sample t test. For between arms analysis, mean difference in the interleukin-6 and interleukin-8 values will be calculated using independent sample t test. Non-parametric statistics will be used if the data is skewed. A cut-off will be calculated for interleukin-6 and interleukin-8 separately using ROC curve analysis. Based on the cut-off, a binary logistic regression analysis will be performed to evaluate the predictive significance of the two treatment arms in reducing the levels of inflammatory markers interleukin-6 and interleukin-8. P-value of < 0.05 will be considered significant. Results will be presented in form of tables & figures. SPSS version 21 will be used for all the statistical analysis.

13. Study committees:

The study will be managed with the help of Graduate Study Committee, Clinical Trial Unit and ORIC of Khyber Medical University, Peshawar, Pakistan.

14. Administrative aspects:

The administrative aspects will be managed with the help of Office of Research, Innovation and Commercialisation (ORIC) of Khyber Medical University, Peshawar, Pakistan.

15. References:

3. Sangeeta S. Metformin and pioglitazone in polycystic ovarian syndrome: a comparative study. The Journal of Obstetrics and Gynecology of India. 2012;62(5):551-6.

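### Does the undefined ROC cut-off and logistic step in Protocol section 12, which the SAP leaves out, call for a change to the plan?

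*Protocol*

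**What the plan says.** Protocol section 12 (Data Analysis Procedure) first plans paired t tests within each arm. It then compares the arms: "For between arms analysis, mean difference in the interleukin-6 and interleukin-8 values will be calculated using independent sample t test". Non-parametric methods are the fallback for skewed data. After these comes the step at issue: "A cut-off will be calculated for interleukin-6 and interleukin-8 separately using ROC curve analysis". The next sentence reads "Based on the cut-off, a binary logistic regression analysis will be performed to evaluate the predictive significance of the two treatment arms", the stated aim being reduction of the two markers. Significance is set at P < 0.05 for all of this, with no ranking among the analyses.

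Protocol section 9 gives the outcome as the change in IL-6 and IL-8. It adds "Other symptoms like hirsutism, polycystic ovaries and serum testosterone levels may decrease and menstrual cycles might become become regular", without defining a responder.

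The SAP, dated 15/03/2018 and written in the past tense, log-transforms IL-6 and IL-8. It lists paired t tests, independent t tests at baseline and after treatment, an independent t test on the change Δ, and Wilcoxon tests for follicle counts. It lists no ROC curve, cut-off or logistic regression, and does not mention that the Protocol had planned them.

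**The concern.** An ROC cut-off cannot be computed from a marker alone. It needs a binary state to discriminate, a rule for picking the point on the curve, and a defined quantity to cut. Section 12 names the markers and leaves the rest open.

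The trial has no group without PCOS ("STUDY DESIGN: Two-Arm Randomized Clinical trial"), so the most obvious binary variable in the dataset is treatment arm. If arm is the state, the cut-off is chosen to separate the arms and the logistic regression then tests whether the arms are separated. That is circular, and the P value can be far too small. Section 12 opens by referring to statistics that "will be used for numeric data generated from our work", which suggests, without stating it, that the cut-off would come from the trial's own women.

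The silent disappearance of the step from the SAP adds to the unease. A reader cannot tell whether it was dropped before the data were seen, dropped afterwards, or run and not reported.

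**Working it through.** **1. Inputs.** There are 51 women per arm, 102 in all (Protocol section 5d), and alpha is 0.05 (Protocol section 12 and SAP), taken as two-sided. The ROC step has no figure of its own to reproduce. The sample size does reproduce if 15% and 40% are read as proportions, with pooled p = (0.15 + 0.40)/2 = 0.275:

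n per arm = (1.960 + 0.842)² × 2 × 0.275 × 0.725 / (0.40 − 0.15)² = 7.85 × 0.39875 / 0.0625 ≈ 50.08, rounded up to 51, so 102.

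**2. Which quantity is cut?** Section 9 defines the outcome as change in level, and section 12 speaks of reducing the levels. Together they point to change. Only its form (absolute, percent or log) is missing.

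**3. Which state?** The text allows three readings.
- A clinical response: the rationale before section 2 says "Interleukin-6 and interleukin-8 may emerge as predictive biomarkers of treatment response". This is the nearest hint, though response is not defined.
- Baseline versus 3 months.
- Treatment arm. No sentence says this.

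**4. What each reading does to the later test of arm.** Null trials were simulated with 51 versus 51 standard normal log values and no marker effect. The cut-off was taken from the data, then a 2×2 logistic test of arm was applied, by Wald z = log(OR)/√(1/a + 1/b + 1/c + 1/d) and by likelihood ratio. There were 20,000 trials per scenario. *Fixed* means the direction of the cut is set beforehand; *either* means the data choose it. Entries are Wald / likelihood-ratio rejection rates at nominal 0.05.

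| State | Rule | Fixed | Either |
|---|---|---|---|
| Arm | Youden | 0.188 / 0.242 | 0.373 / 0.414 |
| Arm | Closest corner | 0.104 / 0.105 | 0.211 / 0.212 |
| Arm | Sensitivity = specificity | 0.049 / 0.049 | 0.048 / 0.048 |
| Response, 15% vs 40% by arm | Youden | 0.054 / 0.077 | 0.070 / 0.078 |
| Response, 15% vs 40% by arm | Closest corner | 0.058 / 0.059 | 0.072 / 0.073 |

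With response at 15% versus 40%, the sensitivity = specificity rule gives 0.059. With response at 27.5% in both arms, all rules lie between 0.038 and 0.063. The response rates are illustrations borrowed from the planning percentages ("With an expected reduction in interleukin-6 and interleukin-8 values of 15% in the Metformin arm" and the 40% for the combination), which the Protocol gives as reductions in the markers.

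For baseline versus 3 months, 5,000 trials per rule gave about 5% to 6% under every rule. This assumes a within-woman correlation of about 0.5 and a common fall of 0.3 SD.

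Inflation above about 8% therefore appears only when arm is the state and the rule is Youden or closest corner.

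**5. Does the step feed anything else?** The between-arm t test in section 12 is planned before the cut-off and does not use it. The SAP's t test on Δ does not use it either. A median split of normal data keeps only φ(0)²/(0.5 × 0.5) = 0.159/0.25 ≈ 0.64 of the information in a t test when the effect is small. That loss would matter only if the split replaced the t test, and it does not.

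**The case for a change.** The strongest case for a change runs as follows. Section 12 plans a significance-tested analysis that cannot be carried out as written. The choices it leaves open move the error rate from 5% to roughly eight times that (0.414/0.05 ≈ 8.3). It then vanishes from the SAP without a word. Moreover, 102 matches a two-proportion formula exactly, and the only binary outcome in the analysis plan is this undefined split, so the step may once have been central. A short note would cost almost nothing, and only the sponsor can say what happened.

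Part of this stands. The state and the rule are missing, the SAP is silent about the omission, and the documents do not show whether the step was withdrawn or run and unreported. Section 12 also never labels the step exploratory.

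The rest does not carry the point to a change in the plan. The high error rates need two choices that no sentence makes, and the nearest hint in the text points to response, where the rate stays near nominal. The match of 102 to a two-proportion formula does not link the sample size to the ROC step, since the 15% and 40% are stated there as reductions in the markers. Declaring the step withdrawn for lack of definition would put a decision and a reason into the SAP that the documents do not support. Whether Δ is on the log scale is a fair question, but a separate one.

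**Conclusion.** The omission is real, but no change to the plan follows. The SAP already lacks the ill-defined step and compares the change in the markers between the arms by t test, which is the comparison that the trial's outcome calls for. No SAP-listed result depends on the cut-off, so defining it or formally deleting it would alter none of them.

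The size of the problem depends on a state and rule that are not given: about 10% to 41% per marker at nominal 5% with arm as the state and a closest-corner or Youden rule, and about 4% to 8% for the other combinations examined. These figures assume 51 per arm, normal log values, no missing data and no true effect. They describe what an analyst could have done and are not evidence of what was done.

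What is left is an unexplained difference between Protocol and SAP about a step outside the between-arm t tests. Should an ROC-based odds ratio appear in a report of this trial, the reader should ask which state and rule produced it before giving its P value any weight.

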EFFECTS OF METFORMIN AND COMBINATION OF METFORMIN AND PIOGLITAZONE ON PLASMA IL-6 AND IL-8 LEVELS IN POLYCYSTIC OVARIAN SYNDROME

Clinical trial registration number: NCT03117517

Date: 15/03/2018

Statistical analysis:

The normality of the data was tested using Kolmogorov-Smirinov and Shapiro-Wilk tests and histograms. FSH, LH, Prolactin, testosterone, IL-6 and IL-8 were not normally distributed and were log transformed for analysis. In the final results log transformed values were back transformed and presented as geometric means and confidence intervals. Patient demographic data were evaluated at baseline as descriptive statistics and presented as mean \pm SD. Wilcoxon signed rank test was used to analyze and compare number of follicles in right and left ovary in the two groups, and also between baseline and follow-up. Results were presented as Median (interquartile range). The baseline data of anthropometric, hormonal and inflammatory markers were compared between the two groups by independent sample t test. Comparison between baseline and after intervention (of 12 weeks) data was done by paired sample t-test for both groups independently. Post intervention comparison between the two groups was also done by independent sample t-test. The change taking place between baseline and after 12 weeks due to intervention was calculated as difference or Δ . Δ was calculated as value at 12 weeks – value at baseline for hormonal, inflammatory and ovarian size variables. The Δ between the two groups was compared by independent sample t-test. P < 0.05 was considered statistically significant. All analyses were performed using SPSS software, version 21 "SPSS (IBM, Armonk, NY, USA).

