Arm#2: 51 women with PCOS will be selected based on the inclusion and exclusion criteria. They will receive metformin and pioglitazone combination according to the body weight with maximum dose of 1000 mg and 30mg (BD) daily.

e. SAMPLING TECHNIQUES: Blood samples will be taken from ante cubital vein after an overnight fast. Samples will be taken from all groups at the initiation and at the end of 3

months. Serum levels LH, FSH, prolactin, testosterone, interleukin-6, interleukin-8 and insulin will be analysed by ELISA method. Fasting glucose will be performed by chemistry analyzer. Evaluation of insulin resistance will be performed by using HOMA-IR Index (Homeostasis model assessment for insulin resistance) with following formula. : HOMA-IR= fasting plasma insulin (µIU/mL) x fasting plasma glucose (mmol/L) /22.5

6. Subject Population:

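### HOMA-IR, the only secondary objective, is named in no analysis; the t-tests that might cover it are unadjusted, and nothing says which one answers the objective

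*SAP*

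**What the plan says.** Protocol section 2 lists one secondary objective: "To evaluate insulin resistance in all the groups at baseline and after 3 months of treatment". Section 5(e) fixes the measure: "Evaluation of insulin resistance will be performed by using HOMA-IR Index", computed as fasting insulin times fasting glucose divided by 22.5. Section 8 has insulin resistance assessed both before treatment and at 12 weeks.

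The analysis text does not pick this up. Section 12 of the protocol names only the two interleukins, within arms ("In each arm the mean difference in the interleukin-6 and interleukin-8 values will be calculated using paired sample t test") and between arms ("For between arms analysis, mean difference in the interleukin-6 and interleukin-8 values will be calculated using independent sample t test"). It adds a general rule for skew: "Non-parametric statistics will be used if the data is skewed".

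The SAP mentions none of insulin resistance, HOMA-IR, insulin or glucose. Its distributional check is general: "The normality of the data was tested using Kolmogorov-Smirinov and Shapiro-Wilk tests and histograms". The outcome of that check is a list: "FSH, LH, Prolactin, testosterone, IL-6 and IL-8 were not normally distributed and were log transformed for analysis". It then describes four t-tests. The baseline between-arm comparison is limited to anthropometric, hormonal and inflammatory markers. The paired within-arm test and the 12-week between-arm test carry no limit. The change score is defined "for hormonal, inflammatory and ovarian size variables" and compared between arms.

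**The concern.** A stated objective should lead to one identifiable analysis, and this one does not. The SAP gives methods for FSH, LH, prolactin, testosterone, follicle counts and ovarian size, none of which is a listed objective, yet it is silent on the one secondary objective. Protocol section 5(e) lists seven ELISA analytes, and the log-transform list contains six of them. The missing one is insulin, an input to HOMA-IR.

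Three things are left open: whether HOMA-IR is compared between arms at all, whether on 12-week values or on change, and on which scale. The two documents also handle skew differently: the protocol by non-parametric tests, the SAP by logs for named variables. An analyst could settle these choices after seeing results. Whichever t-test is chosen, the baseline HOMA-IR already collected is either ignored or merely subtracted, which can waste information.

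**Working it through.** **1. The plan's own figure.** The only sample-size figure is 102 women, for IL-6 and IL-8 (protocol section 5(d)). Treating 15% and 40% as two proportions, with two-sided alpha 0.05, power 0.80 and mean proportion 0.275:

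n per arm = (1.960 + 0.842)² × 0.275 × 0.725 × 2 / 0.25² = 50.08, so 51 per arm and 102 in total.

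The figure reproduces, but it says nothing about HOMA-IR.

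**2. Which SAP analyses can include HOMA-IR.**

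| SAP analysis | Stated scope | Covers HOMA-IR? |
|---|---|---|
| Baseline, between arms | anthropometric, hormonal, inflammatory | only if hormonal is stretched |
| Paired, within arm | none stated | can be read so |
| 12-week, between arms | none stated | can be read so |
| Change, between arms | hormonal, inflammatory, ovarian size | only if hormonal is stretched |
| Log-transform list | six named variables | no |

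HOMA-IR therefore gets one between-arm treatment comparison on the broad reading and two on the broadest. None is marked as the answer to the objective, and none adjusts for baseline.

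**3. What the choice could cost (illustration).** From the documents: 51 per arm and alpha 0.05 (two-sided assumed). Assumed: log-normal HOMA-IR, log-SD s = 0.5 or 0.7, baseline to 12-week log-scale correlation r = 0.4 or 0.6. The falls of 15% and 40% are borrowed from the interleukins, so the 12-week multipliers are a = 0.85 and 0.60.

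Normal-approximation check at s = 0.7, r = 0.4, in units of the baseline mean, with CV² = exp(0.49) − 1 = 0.632:

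- Raw 12-week t-test: z = 0.25 / √[0.632 × (0.85² + 0.60²) / 51] = 0.25 / 0.116 = 2.16; power ≈ Φ(2.16 − 1.96) = 0.58.
- Raw change t-test: variance per arm = CV²(1 + a²) − 2a[exp(rs²) − 1], which is 0.721 (a = 0.85) and 0.600 (a = 0.60). z = 0.25 / √(1.321 / 51) = 1.55; power ≈ Φ(−0.41) = 0.34.
- Log-scale baseline-adjusted model: z = ln(0.85/0.60) / [0.7 × √(1 − 0.16) × √(2/51)] = 0.348 / 0.127 = 2.74; power ≈ Φ(0.78) = 0.78.

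Subtracting baseline hurts here because it adds variance. In the metformin arm the change has variance 0.721, against 0.632 × 0.85² = 0.457 for the 12-week value alone.

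Simulated power (6,000 to 8,000 trials per setting; repeat runs agree to within about 0.02):

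| s, r | Raw change t | Raw 12-week t | Raw, baseline-adjusted | Log, baseline-adjusted |
|---|---|---|---|---|
| 0.7, 0.4 | 0.36 | 0.61 | 0.66 | 0.77 |
| 0.7, 0.6 | 0.47 | 0.61 | 0.75 | 0.88 |
| 0.5, 0.4 | 0.66 | 0.90 | 0.94 | 0.97 |
| 0.5, 0.6 | 0.80 | 0.91 | 0.98 | 0.99 |

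Subtracting columns: the SAP's two raw-scale tests differ from each other by 11 to 25 points. Baseline adjustment on the raw scale adds 4 to 14 points over the 12-week test and 18 to 30 over the change test. Moving to logs adds a further 1 to 13.

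**4. Sensitivity to the effect.** With a 15% fall on metformin and a further 20% relative fall on the combination, power is 0.19 to 0.48 for raw change and 0.41 to 0.79 for the log-scale adjusted model. In a separate simulation of change scores alone (s from 0.4 to 0.8, r from 0.3 to 0.7), type I error was 0.046 to 0.053 on both raw and log scales.

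**The case against.** The strongest reply is that HOMA-IR is not left out. Two of the SAP's t-tests carry no restriction on variables, so it has a within-arm test and a 12-week between-arm test. The objective speaks of evaluating insulin resistance in all groups at two times and does not expressly promise a between-arm contrast. The hypothesis concerns the interleukins only, and paired tests could satisfy the objective as worded. This stands. A reader might infer that HOMA-IR falls outside every analysis, and the documents do not support that.

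A reader might also infer that HOMA-IR would be analysed on the wrong scale. That is not shown either. The SAP reports the normality check in the past tense and for the data generally, so absence from the log list may mean that HOMA-IR passed, or that it was overlooked. No distribution is given, and the protocol has a fallback for skewed data.

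Finally, setting raw change against log-scale adjustment compares the weakest option with the strongest. This also stands: much of that gap comes from how baseline is used, and with adjustment on both sides the scale alone accounts for 1 to 13 points. The use of unadjusted t-tests is also not peculiar to HOMA-IR.

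None of this supplies a rule for which test answers the objective. In a two-arm randomised trial, within-arm tests alone do not compare the treatments.

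**Conclusion.** The point holds as a gap in specification with a better method available at almost no cost. HOMA-IR is named in no analysis, and neither it nor insulin is in the log-transform list. Read generously, the SAP gives it one or two unadjusted between-arm t-tests with no order of precedence.

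Under the assumptions above, a single baseline-adjusted model is more powerful than either raw-scale t-test in every setting examined. The power figures illustrate the direction and rough size only: the log-normal shape, SDs and correlations are assumed, the effects are borrowed from other outcomes, and the trial was not sized for HOMA-IR. The cost is lost precision and an open choice of test, not a raised false-positive rate for any one test fixed in advance. The primary interleukin results are unaffected.

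**What to change.** Add to the SAP that the secondary analysis compares 12-week HOMA-IR between arms in one linear model adjusted for baseline HOMA-IR, reported with a 95% CI and labelled secondary. Describe any within-arm or change-score result for HOMA-IR as supportive.

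State that the SAP's own normality check is applied to HOMA-IR and fasting insulin and report the outcome. If they are skewed, fit the model on the log scale with log baseline as covariate and report a geometric mean ratio, in keeping with the SAP's geometric-mean reporting for IL-6 and IL-8. Say that for this endpoint this replaces the protocol's non-parametric rule, so that only one rule applies. If HOMA-IR results had been seen before the model was chosen, say so in the report.

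The cost is a few sentences in the SAP and one extra model in software already in use, on data the protocol already collects. No stated figure changes, including the sample size.

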6.1 Target population

Women with PCOS visiting the outpatient department of participating hospitals.

6.2 SAMPLE SELECTION:

Inclusion criteria:

PCOS women will have the following inclusion criteria: age group 20 - 40 years, oligoanovulation, hirsutism, elevated serum testosterone levels, menstrual cycle irregulary. Diagnosis of PCOS on ultrasound will be made on the basis of European Society of Human Reproducion and Embryo/ American Society of Reproductive Medicine (ESHRE/ASRM criteria, 2003) according to which 10 or more follicular cysts ranging in size from 2-9 mm or increased ovarian volume of 10 cm in maximal diameter.

Exclusion criteria:

Women with previous history of cushing syndrome, hyperprolactinemia, late onset congenital adrenal hyperplasia, androgen-producing tumors, pregnancy or those taking medications that alters the biochemical or hormonal profile will be excluded by clinical and medical examination.

6.3 Screening:

Before the study-specific screening and investigations, patient will sign a written informed consent and the investigator will also sign the consent with date.

6.4 Registration:

Subjects will be registered before starting study treatment and a registration number will be allotted. Requests for registration will only be accepted from authorized investigators at sites that have received ethical approval. Treatment would be planned to start after registration. Registration would be done according to the instructions in the protocol only after all screening assessments have been performed and the responsible investigator has both verified the subject's eligibility and signed the completed registration form.

[figure not shown]
Once the registration process has completed as per the instructions in the protocol, the subject will be assigned a subject, study number, and written confirmation of registration will be provided to the site. Individuals must be registered once in this trial.

6.5 Randomization:

Randomization will be performed using Block Randomization technique using online software Sealed Envelope.

Appendix 1

Study Schema

7. Data Collection Procedure:

7.1 PATIENT RECUIREMENT:

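### The SAP appears to compare follicle number between unmatched randomised arms with the Wilcoxon signed rank test, and neither document names a rank test for independent groups

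*SAP*

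**What the plan says.** The SAP (Statistical analysis) deals with follicle number in one sentence: "Wilcoxon signed rank test was used to analyze and compare number of follicles in right and left ovary in the two groups". The sentence goes on to add baseline versus follow-up as a further use of the same test. The summary is the median with interquartile range, so follicle number is treated as non-normal.

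The protocol describes a "Two-Arm Randomized Clinical trial" (section 5a) with 51 women planned per arm. Section 6.5 says "Randomization will be performed using Block Randomization technique". No matching or pairing of women is described.

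On non-parametric methods, protocol section 12 says only "Non-parametric statistics will be used if the data is skewed", and it names no test. Section 9 mentions the ovaries only in passing: "Other symptoms like hirsutism, polycystic ovaries and serum testosterone levels may decrease".

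**The concern.** The signed rank test works on differences within pairs. Baseline and 12-week counts from one woman form a pair. A woman in the metformin arm and a woman in the combination arm do not.

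The SAP sentence introduces the comparison over time as an additional one. The comparison before it therefore reads most naturally as arm versus arm, with right and left ovary as the two variables analysed. On that reading a paired test is assigned to unpaired data.

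If it was run that way, each woman was set against whoever shared her row in the other arm. The P-value then depends on how the file was ordered, and women without a partner row drop out when arm sizes differ. If it was not run that way, the reader cannot tell which test compared the arms.

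**Working it through.** **1. Does another sentence supply a between-arm test for follicle number?**

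| Place | Between-arm provision | Covers follicle number? |
|---|---|---|
| SAP, baseline comparison | Independent t-test for anthropometric, hormonal and inflammatory markers | Not listed |
| SAP, 12-week comparison: "Post intervention comparison between the two groups was also done by independent sample t-test" | Independent t-test, no variables listed | Not stated; a median (IQR) summary does not fit a t-test |
| SAP, comparison of change (Δ), defined "for hormonal, inflammatory and ovarian size variables" | Independent t-test | Ovarian size is listed, follicle number is not |
| Protocol section 12, between arms | Independent t-test | IL-6 and IL-8 only |
| Protocol section 12, skewed data | Unspecified non-parametric statistics | No test named |

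None does.

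**2. The three readings of the sentence**

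- *Arm versus arm, as named.* The test is wrong for the design.
- *Slip for rank-sum.* The intended test is right but the SAP names another.
- *Right versus left ovary within each woman.* The test is right, but the between-arm comparison has no clearly specified test.

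**3. Why row order matters**

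Signed rank: for row i, D_i = X_i − Y_i. Rank the non-zero |D_i| and sum the ranks where D_i > 0. Each D_i depends on which Y shares the row with X_i, so re-ordering one arm changes the statistic.

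Rank-sum: U = R₁ − n₁(n₁ + 1)/2, where R₁ is the sum of arm 1's ranks in the pooled sample. Row order does not enter.

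**4. Size, by simulation**

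The plan gives no figure to reproduce. From the documents: 51 per arm and the 0.05 threshold. Assumed: rounded normal counts with mean 12 and SD 2 to 6.

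Type I error, no true difference, 4,000 trials per SD:

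| SD | Signed rank, random row order | Rank-sum | Signed rank, both arms sorted by count |
|---|---|---|---|
| 2 | 5.0% | 4.6% | 66% |
| 3 | 4.7% | 5.0% | 70% |
| 4 | 4.9% | 4.5% | 73% |
| 6 | 4.7% | 4.8% | 75% |

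The last column needs both arms sorted by count, which nothing in the documents suggests.

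Same data under two random row orders, share of trials with opposite signed rank verdicts at 0.05 (2,500 trials per cell):

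| True difference | SD 2 | SD 3 | SD 4 |
|---|---|---|---|
| 0 | 2.2% | 2.7% | 2.5% |
| 0.3 SD | 7.4% | 7.9% | 9.6% |
| 0.4 SD | 9.6% | 9.5% | 9.5% |
| 0.5 SD | 9.4% | 7.6% | 9.0% |
| 0.6 SD | 6.0% | 4.8% | 6.1% |

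One fixed dataset: 51 rounded normal quantiles per arm, means 12 and 10.8, SD 3, so the difference is (12 − 10.8)/3 = 0.4 SD. Rank-sum P = 0.058. Over 5,000 row orders the signed rank P ran from 0.006 to 0.224 (central 95%: 0.019 to 0.122), with 37% of orders below 0.05.

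Power at 0.5 SD (SD 3, 4,000 trials); the unequal arms are hypothetical:

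| Arms | Women dropped by pairing | Signed rank | Rank-sum |
|---|---|---|---|
| 51 / 51 | 0 | 68.5% | 68.4% |
| 51 / 46 | 51 − 46 = 5 | 62.4% | 64.8% |
| 51 / 41 | 51 − 41 = 10 | 57.7% | 62.9% |

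**5. Check with a different count distribution**

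Negative binomial counts, dispersion 8, 51 per arm, 4,000 runs. With equal means the signed rank test rejected in 5.5% and rank-sum in 5.8%. With means of 10 and 8 the figures were 60% and 59%. In one dataset with rank-sum P = 0.049, re-ordering one arm moved the signed rank P over 0.026 to 0.139 (central 95% of 5,000 orders), with 19% below 0.05. The conclusion is the same.

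**The case against.** The arm-versus-arm reading can be contested. Where the SAP clearly compares arms it says *between* the two groups; the follicle sentence says *in* them, which could mean within each group. Right versus left ovary would then be the first comparison, and both uses of the test would be valid. The authors also chose independent-sample tests for every other arm comparison, so a naming slip is more plausible than women actually being paired by row.

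The numerical harm is modest too. Average type I error and equal-arm power are unchanged, and the wide P-value ranges come from datasets chosen near the threshold. The plan is for equal arms. A saved data file would reproduce its own P-value exactly. Follicle number is not a stated endpoint.

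Most of this stands as a limit on importance. It does not remove the defect. On the right-versus-left reading the between-arm test is still not clearly specified, and a slip still leaves the wrong test named. A P-value that reproduces only from one arbitrary file order is not a property of the data. The objection is also right that P-values need replacing only if the signed rank test was run across arms, and that testing change in follicle number is a preference.

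**Conclusion.** The concern holds. As most naturally read, the SAP assigns a paired test to two independent arms, and on either alternative reading the sentence still needs repair. Confidence in the reading is medium, because the documents do not show what was run.

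If the test was run across arms, the fault is arbitrariness, not inflated error. Two row orders of the same data would disagree at 0.05 in about 2–3% of trials with no effect and 5–10% with a true difference of 0.3–0.6 SD. These figures assume rounded normal counts with mean 12, SD 2 to 4, 51 women per arm, and row order unrelated to the counts.

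The effect is confined to follicle number. The IL-6, IL-8 and insulin resistance analyses are untouched. This should be corrected, but it does not threaten the trial's main conclusions.

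**What to change.** - Name the Mann-Whitney (Wilcoxon rank-sum) test for the between-arm comparison of follicle number, separately for each ovary. Apply it to the 12-week count or, preferably, to the change from baseline, which would parallel the SAP's Δ analysis of other variables.
- Keep the signed rank test for baseline versus 12 weeks within each arm.
- If right versus left ovary was meant, say so and add the between-arm test.
- Confirm which test was actually run. If it was the signed rank test across arms, replace those P-values.

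The cost is one SAP sentence and, if needed, a rerun of a standard SPSS procedure. The SAP is written in the past tense, so any replaced P-value should be reported as a correction made after the analysis.
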